9.7 DATA ANALYSIS

The two cohorts will be analysed separately

- Uncommon mutations
- Sequencing of osimertinib after afatinib

The primary endpoint for both cohorts is time on treatment. Kaplan-Meier estimates will be calculated. In addition, the median will be tabulated along with the two-sided 95% confidence interval, using Greenwood's variance estimate.

The following additional endpoints will be analyzed similarly to the primary endpoint.

- overall survival
- time on treatment until failure of second-line (uncommon cohort only)

Patients who were not known to have discontinued treatment will be censored on the date they were last verified to have been on treatment.

A second round of data collection for additional follow-up may be performed in case a substantial proportion of patients had not discontinued treatment before the estimated median time on treatment at the time of the primary data collection.

Best overall response will be tabulated, as will the following:

- demographics
- disease characteristics
- methodology and material used for mutation classification
- anti-cancer drugs used prior to, or after EGFR-TKI (uncommon cohort only).

These endpoints will be analyzed descriptively.

Within the sequencing cohort, the proportion of patients with different types of resistance mutations observed at the time of discontinuation of osimertinib will be categorized and tabulated.

In this study, data will be gathered retrospectively from patients treated within the conditions of the approved marketing authorization of afatinib. Drug exposure during pregnancy, ADRs with causality to Gilotrif (serious or non-serious) and all fatal AEs will be reported to PV on the NIS AE form - excluding deaths to PD of the underlying malignancy. Safety data will be reviewed and analysed as part routine global pharmacovigilance procedures. All adverse events/reactions collected for the study per protocol will be summarised in the final study report.

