- if “Was mutational status re-evaluated at at stop of second-line treatment (or within end of observation, in case second-line treatment was not discontinued)?” [**MUT2. MUT2_reeval_stop**] = “No” OR if “Any changes in EGFR mutations with respect to start of second-line treatment?” [**MUT2. MUT2_changes_stop**] = “UNK”, patients will be classified as “Unknown EGFR mutational status”
- if “Any changes in EGFR mutations with respect to start of second-line treatment?” [**MUT2. MUT2_changes_stop**] = “No”, then the patient’s EGFR mutational status at second-line treatment stop/end of observation will be imputed as the same patient’s EGFR mutational status at second-line treatment start (as defined before)
- if “Any changes in EGFR mutations with respect to start of second-line treatment?” [**MUT2. MUT2_changes_stop**] = “Yes”, then the patient’s EGFR mutational status at second-line treatment stop/end of observation will be retrieved from the fields [**MUT2. MUT2_mut_stop**, **MUT2_mut_stop_ex20_sp**, **MUT2_mut_stop_sp**, **MUT2_concom_mut_stop**]

Acquired EGFR mutations at second-line treatment stop/end of observation

For both cohorts, the mutations found at stop of second-line treatment/end of observation (i.e. the options selected in the field [**MUT2. MUT2_mut_stop**]) will be compared to the mutations found at start of second-line treatment (i.e. the options selected in the field [**MUT2. MUT2_mut_start**]). The mutations found at second-line treatment stop/end of observation that were not present at start of second-line treatment will be classified as acquired EGFR mutations.

Classification of EGFR uncommon mutations (according to Yang's classification) for exploratory analyses

According to the MUTATIONS form, considering the EGFR mutational status at first- and second-line treatment start (but considering only lines containing EGFR-TKIs), the following definitions will be applied to classify patients' mutational status with respect to EGFR gene:

- **T790M-positive:** patients having T790M at start of either first- or second-line EGFR-TKI, but excluding patients developing acquired T790M at second-line osimertinib start;
- **Exon 20 insertion-positive:** patients having any type of exon 20 insertion at start of either first- or second-line EGFR-TKI, excluding patients included in group "a");

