- **Major uncommon mutations:** patients having either G719X and/or L861Q and/or S768I mutations at start of either first- or second-line EGFR-TKI, excluding patients included in groups "a)" or "b");
- **Others:** patients not included in groups "a)", "b)", or "c");
- **Compound mutations:** patients having more than one mutation of any type (including also common mutations).

The same patient cannot be included in more than one of the following groups, which are mutually exclusive: a), b), c), d). On the contrary, the same patient can be included in group e) and also in another group a) or b) or c) or d).

Source: Chih-Hsin Yang J, Schuler M, Popat S, Miura S, Heeke S, Park K, Märten A, Kim ES, Afatinib for the Treatment of Non-Small Cell Lung Cancer Harboring Uncommon EGFR Mutations: A Database of 693 Cases, *Journal of Thoracic Oncology* (2020), doi: <https://doi.org/10.1016/j.jtho.2019.12.126>.

Classification of EGFR uncommon mutations at first-line treatment start

The same 5 classes described above will be considered, but considering only EGFR mutational status at first-line treatment start (see algorithm described before), and without restrictions on type of treatment line.

Classification of EGFR uncommon mutations at second-line treatment start

The same 5 classes described above will be considered, but considering only EGFR mutational status at second-line treatment start (see algorithm described before), and without restrictions on type of treatment line.

In particular, "T790M-positive" group includes also patients developing acquired T790M at second-line osimertinib start, while excludes patients with T790M acquired only and treated with osimertinib. However, if the patient had also additional acquired mutations at start of second-line osimertinib (and not only acquired T790M), then the patient will not be excluded.

Only patients with Number of NSCLC treatment lines (as defined before) > 1 and [**MUT2. MUT2_reeval**] = "Yes" will be considered.

Patients without mutations at second line treatment start will not be included in "Others".

Classification of EGFR uncommon mutations at second-line treatment stop/end of observation

The same 5 classes described above will be considered, but considering only EGFR mutational status at second-line treatment stop/end of observation (see algorithm described before), and without restrictions on type of treatment line.

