Only patients with Number of NSCLC treatment lines (as defined before) > 1 and [**MUT2. MUT2_reeval_stop**] = "Yes" will be considered.

Time on treatment with index therapy EGFR-TKI for UNCOMMON MUTATIONS COHORT

The following patients will be considered as having the event “treatment discontinuation”:

- patients with discontinuation of index EGFR-TKI treatment, ie. those with discontinuation defined as “Treatment discontinued?” [EAD. EAD_treat_disc] = “Yes” in the latest record of the EGFR-TKI ADMINISTRATION DETAILS form referred to the index EGFR-TKI treatment (as defined before). For these patients, the time to event will be computed as the difference between the field “Stop date with this dose” [EAD. EAD_stop_date] of the above-mentioned record and the start date of the Index EGFR-TKI therapy (as defined before) + 1 day;
- deceased patients at time of inclusion in the study, ie. those with [PI. PI_pt_class] = “Deceased patient”. For these patients, the time to event will be computed as the difference between the “Date of death” [PI. PI_date_death] and the start date of the Index EGFR-TKI therapy (as defined before) + 1 day.

The same patient could have multiple events, but for the purpose of the analysis only the earliest event will be considered.

Other patients will be considered as censored observations. The following situations might be observed:

- non-deceased patients with evidence of ongoing treatment at end of observation, ie. those with [PI. PI_pt_class] = (“Living patient” OR “Untraceable patient”) and with “Treatment discontinued?” [EAD. EAD_treat_disc] = “No” in the latest record of the EGFR-TKI ADMINISTRATION DETAILS form referred to the index EGFR-TKI treatment (as defined before). For these patients, the time to censoring will be computed as the difference between the end of observation date (as defined later) and the start date of the Index EGFR-TKI therapy (as defined before) + 1 day;

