- absolute and relative frequency of “Methodology used for mutation testing”, with details of ARMS, sequencing, NGS (according to the fields [*Second-line treatment period / MUT2. MUT2_meth_start, MUT2_meth_start_sp, MUT2_meth_ARMS, MUT2_meth_ARMS_sp, MUT2_meth_seq, MUT2_meth_seq_sp, MUT2_meth_NGS, MUT2_meth_NGS_sp*])

Descriptives and percentages will be calculated over the number of ELIGIBLE PATIENTS in the cohort, considering only patients with Number of NSCLC treatment lines >1 (see “Computed variables” chapter) with “Was mutational status re-evaluated at start of second-line treatment” [*Second-line treatment period / MUT2. MUT2_reeval*] = “Yes”.

[figure not shown]

Table 15-UNC. Mutations at second-line treatment stop/end of observation (ELIGIBLE PATIENTS of the Uncommon Mutation Cohort)

The table will provide:

- absolute and relative frequency of patients according to EGFR mutational status at second-line treatment stop/end of observation (see “Computed variables” chapter);
- absolute and relative frequency of patients according to Classification of EGFR uncommon mutations at second-line treatment stop/end of observation (see “Computed variables” chapter);
- absolute and relative frequency of patients according to acquired EGFR mutations at second-line treatment stop/end of observation (see “Computed variables” chapter);
- absolute and relative frequency of patients according presence/absence of other mutated genes and detail of mutations at second-line treatment stop/end of observation (according to the fields [*Second-line treatment period / MUT2. MUT2_oth_gene_stop_YN* (*), *MUT2_oth_gene_stop, MUT2_oth_gene_stop_sp*]).

(*) in case [*MUT2_oth_gene_stop_YN*] = “No”, then the patient’s mutational status for other genes at second-line treatment stop/end of observation will be imputed as the same patient’s mutational status for other genes at second-line treatment start.

Descriptives and percentages will be calculated over the number of ELIGIBLE PATIENTS in the cohort, considering only patients with Number of NSCLC treatment lines >1 (see “Computed variables” chapter) with “Was mutational status re-evaluated at stop of second-line treatment [...]” [*Second-line treatment period / MUT2. MUT2_reeval_stop*] = “Yes”.

Table 16-UNC. Approaches for detection of mutations at second-line treatment stop/end of observation (ELIGIBLE PATIENTS of the Uncommon Mutation Cohort) – Secondary objective #3

The table will provide:

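### At second-line stop, the residual class 'Others' takes in re-tested patients with no EGFR mutation or only Del19/L858R (minor; descriptive tables only)

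*SAP*

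**What the plan says.** SAP section 3 sets up five classes: a) T790M-positive, b) exon 20 insertion, c) major uncommon (G719X, L861Q, S768I), d) *Others* and e) compound. Classes a to d are mutually exclusive; e overlaps with them. Class d is defined only as "patients not included in groups" a, b or c. It does not require that any uncommon mutation be present.

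The classes are then reused at single time points:

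- Second-line start: "Patients without mutations at second line treatment start will not be included in" *Others*.
- Second-line stop or end of observation: "The same 5 classes described above will be considered, but considering only EGFR mutational status at second-line treatment stop/end of observation". The only restriction added is "Only patients with Number of NSCLC treatment lines (as defined before) > 1 and" a positive answer in the field for re-evaluation at stop.

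SAP 4.1.3 has Table 15-UNC report "absolute and relative frequency of patients according to Classification of EGFR uncommon mutations at second-line treatment stop/end of observation". Its layout in SAP 5.1.3 gives five classification rows, with none for no mutation, common mutation only or unknown status. SAP 4.2.3 defines Table 13-SEQ solely by reference to the corresponding table of the other cohort. The classification is declared not applicable only for Table 9-SEQ.

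**The concern.** A class read as a group of uncommon mutations should hold patients in whom one was found. The SAP recognises this at second-line start, where it removes patients without mutations from *Others*. The adjacent rule for second-line stop has no such sentence and nothing explains the difference. A programmer cannot safely assume that an exclusion stated at one of two neighbouring time points also applies at the other.

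Common-only results are a second gap, present at both time points. They are a natural finding in the sequencing cohort, where SAP 2.1 (criterion 5) requires Del19 or L858R at first-line start for every patient. A patient who no longer shows T790M when osimertinib stops, and has only the original common mutation, has no row but *Others*.

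At stake is the meaning of one row in Tables 15-UNC and 13-SEQ, and of one block in Table 17-UNC, whose title concerns the mutation type detected by each technique. In that block, techniques would be listed against a class that includes patients in whom no uncommon mutation was detected.

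**Working it through.** The plan gives no figure to reproduce here. The check is to apply the rules in the order a, b, c, then d as the remainder, to patients with more than one line who were re-tested at stop.

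| EGFR status at stop | Class as written | Class after the fix |
|---|---|---|
| None found | Others | No uncommon mutation detected |
| Del19 only | Others | No uncommon mutation detected |
| L858R only | Others | No uncommon mutation detected |
| Sequencing patient, Del19, T790M no longer found | Others | No uncommon mutation detected |
| E709X | Others (as intended) | Others |
| G719X | Major uncommon | Major uncommon |
| Re-tested, status unknown | Others, unless treated as missing | Unknown |
| Del19 with T790M acquired before osimertinib and still present | Not settled by the text | To be stated |

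Two rows need explanation.

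**Unknown status.** SAP section 3 assigns an unknown status when the answer to "Any changes in EGFR mutations with respect to start of second-line treatment" is unknown. A re-tested patient can also receive it when no change is recorded from a start status that was itself unknown. The text on the stop classification does not say what happens to these patients.

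**Persisting T790M.** Class a, as first defined, leaves out patients who develop acquired T790M at the start of second-line osimertinib. The stop rule neither repeats nor lifts this. If it carries over, a sequencing patient with T790M still present is not in class a and falls to *Others* unless b or c applies. If it does not carry over, the patient is T790M-positive.

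**Size.** Let p be the share of re-tested patients with a genuine other uncommon mutation and u the share with no EGFR mutation or only Del19/L858R. Then

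reported *Others* = p + u.

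The denominator is all re-tested patients, so u leaves the percentages for b and c as they are. The documents give neither p nor u at second-line stop. To show sensitivity only, take p = 10%, the share with other uncommon mutations among TKI-naïve patients in Protocol 9.5, and assume u:

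- u = 5%: 10% + 5% = 15%
- u = 10%: 10% + 10% = 20%
- u = 20%: 10% + 20% = 30%
- u = 30%: 10% + 30% = 40%

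Both inputs are assumptions at this time point. The 10% describes patients before TKI treatment.

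**Other time points.** At second-line start the existing exclusion covers patients without mutations but not those with Del19/L858R alone. At first-line start, SAP 2.1 (criterion 5) and the index-therapy rule in section 3 admit patients whose uncommon mutation is recorded only at second-line start. Such a patient can be common-only at first line and so fall into *Others* in Table 9-UNC.

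**The case against.** Several points on the other side stand.

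- **Mutation detail is reported elsewhere in the same table.** Protocol 9.7 promises that "the proportion of patients with different types of resistance mutations observed at the time of discontinuation of osimertinib will be categorized and tabulated". A reader might infer that this breakdown is lost. It is not: besides the five-class block, Table 15-UNC lists each EGFR mutation separately, including Del19, L858R, other EGFR mutations and unknown status, and has blocks for acquired mutations and other genes. Table 13-SEQ inherits these.
- **Unknown status is arguable.** The opening of SAP section 4 excludes patients with missing data from the analysis of that variable, which could remove unknowns from the classification. Against that, unknown is a defined level with its own row in the status block. The text should settle it, but the point does not depend on it.
- **Table 17-UNC is judged from its layout.** The section 4 description of that table is not visible in the public text and may restrict its population.
- **The classes are secondary in purpose.** The parent classification is headed as exploratory, and Tables 15-UNC, 17-UNC and 13-SEQ carry no objective label.

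A reader might also try to size the effect from Protocol 7.2, where T790M positivity was 66% by ddPCR and 24% by Cobas. That would imply 34% to 76% negative (100% − 66% and 100% − 24%) and a 42-point swing in *Others* through assay choice (76% − 34%). The documents do not support this. Those figures concern patients who had progressed on an EGFR TKI, not patients at the end of second-line treatment. A T790M-negative patient with an exon 20 insertion or a major uncommon mutation belongs to class b or c. In the sequencing cohort it is not even clear that persisting T790M keeps a patient out of *Others*.

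**Conclusion.** The rule as written gives a wrong class count at second-line stop whenever a re-tested patient has no EGFR mutation or only Del19/L858R. The common-only part also applies at second-line start. The excess in *Others* equals the share of such patients and is zero if there are none; its size cannot be derived from the documents. The conclusion rests on reading class d literally as a residual and on the absence at stop of the exclusion stated at start. It is firm for Table 15-UNC and, through the cross-reference, for Table 13-SEQ. For Table 17-UNC it rests on the layout.

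Severity is minor. Only descriptive classification rows are affected. Time on treatment, overall survival, time to second-line treatment failure and overall response rate do not use this class.

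**What to change.** In SAP section 3, for all single-time-point classifications (first-line start, second-line start, second-line stop):

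1. Define *Others* as at least one EGFR mutation other than Del19/L858R that is not in classes a to c.
2. Add a row for no uncommon EGFR mutation detected (none, or Del19/L858R only).
3. State that unknown EGFR mutational status is not part of *Others*, and show it in its own row.
4. State at stop which class holds T790M that was acquired before second-line osimertinib and persists.

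Carry the change into Tables 9, 11, 12, 14, 15 and 17-UNC and Tables 11 and 13-SEQ. The cost is a few sentences in section 3, two extra table rows and the matching programming. No new data are needed.

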9.2 SETTING

It is planned that around 65 study centres in up to 11 countries will be participating in this non-interventional study and at least 200 consecutive eligible patients in the sequencing cohort and approximately 250 patients in the uncommon cohort from up to 80 sites will be enrolled to the study. Data extraction from local data bases might be used when possible. Every patient who fulfils inclusion and exclusion criteria and agree to participate in the study (if a written informed consent is required for this NIS by local regulation and legal requirement) will be selected until the required sample size is achieved. Deceased patients should be enrolled whenever possible. This has to be discussed with the local authorities. Investigators who fail to enrol at least one patient in the first 8 weeks of the study may be excluded from further participation. If enrolment is delayed additional countries and centres may be recruited.

To avoid differential centre influence on study results, permission to enrol more than 15 patients per site and cohorts must be obtained from the CTL.

Recruiting of patients for this study is competitive, i.e., recruitment will stop at all centres when it is determined that a sufficient number of patients have been enrolled. Investigators will be notified when the appropriate number of patients has been enrolled and recruitment is complete, and will not be allowed to recruit additional patients for this study.

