- non-deceased patients with unknown information on treatment interruption at end of observation, ie. those with [PI. PI_pt_class] = (“Living patient” OR “Untraceable patient”) and with “Treatment discontinued?” [EAD. EAD_treat_disc] = “UNK” in the latest record of the EGFR-TKI ADMINISTRATION DETAILS form referred to the index EGFR-TKI treatment (as defined before). For these patients, the time to censoring will be computed as the difference between the greatest start date [EAD. EAD_start_date] of the EGFR-TKI ADMINISTRATION DETAILS form referred to the index EGFR-TKI treatment (as defined before) and the start date of the Index EGFR-TKI therapy (as defined before) + 1 day.

Time on treatment for SEQUENCING COHORT

The following patients will be considered as having the event “osimertinib treatment discontinuation after switch from afatinib”:

- patients with discontinuation of osimertinib treatment, ie. those with discontinuation defined as “Treatment discontinued?” [OAD. OAD_treat_disc] = “Yes” in the latest record of the OSIMERTINIB ADMINISTRATION DETAILS form. For these patients, the time to event will be computed as the difference between the field “Stop date with this dose” [OAD. OAD_stop_date] of the above-mentioned record and the start date of the first-line therapy (as defined before) + 1 day;
- deceased patients at time of inclusion in the study, ie. those with [PI. PI_pt_class] = “Deceased patient”. For these patients, the time to event will be computed as the difference between the “Date of death” [PI. PI_date_death] and the start date of the first-line therapy (as defined before) + 1 day.

The same patient could have multiple events, but for the purpose of the analysis only the earliest event will be considered.

Other patients will be considered as censored observations. The following situations might be observed:

- non-deceased patients with evidence of ongoing treatment at end of observation, ie. those with [PI. PI_pt_class] = (“Living patient” OR “Untraceable patient”) and with “Treatment discontinued?” [OAD. OAD_treat_disc] = “No” in the latest record of the OSIMERTINIB ADMINISTRATION DETAILS form. For these patients, the time to censoring will be computed as the difference between the end of observation date (as defined later) and the start date of the first-line therapy (as defined before) + 1 day;

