- non-deceased patients with unknown information on second-line treatment interruption at end of observation, ie. those with [**PI. PI_pt_class**] = (“Living patient” OR “Untraceable patient”) and “Ongoing at end of observation?” [**Second-line treatment period / TREAT. TREAT_ongoing**] = “UNK”. For these patients, the time to censoring will be computed as the difference between the latest start date of the most recent regimen/posology(*) and the start date of the first-line therapy (as defined before) + 1 day.

(*) it will correspond to the greatest start date among:

- the field “Start date of this line” [**Second-line treatment period / TREAT. TREAT_start_date**]
- the greatest start date [**EAD. EAD_start_date**] of the EGFR-TKI ADMINISTRATION DETAILS form.

Overall Survival for UNCOMMON MUTATION COHORT

For deceased patients at time of inclusion in the study (ie. those with [PI. PI_pt_class] = “Deceased patient”), the time to event will be computed as the difference between the “Date of death” [PI. PI_date_death] and the start date of the Index EGFR-TKI therapy (as defined before) + 1 day.

Other patients will be considered as censored observations. The following situations might be observed:

- alive patients at end of observation, ie. those with [PI. PI_pt_class] = “Living patient”. For these patients, the time to censoring will be computed as the difference between the end of observation date (as defined later) and the start date of the Index EGFR-TKI therapy + 1 day;
- untraceable patients at end of observation, ie. those with [PI. PI_pt_class] = “Untraceable patient”. For these patients, the time to censoring will be computed as the difference between the latest date when the patient was known to be alive (ie. [PI. PI_date_alive]) and the start date of the Index EGFR-TKI therapy + 1 day.

Overall Survival for SEQUENCING COHORT

For deceased patients at time of inclusion in the study (ie. those with [PI. PI_pt_class] = “Deceased patient”), the time to event will be computed as follows:

- for **OS from afatinib start**, as the difference between the “Date of death” [PI. PI_date_death] and the Start date of first-line therapy (as defined before, namely afatinib) + 1 day;

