- for **OS from osimertinib discontinuation**, as the difference between the “Date of death” [PI. PI_date_death] and the Stop date of second-line therapy (as defined before, namely osimertinib) + 1 day. This algorithm will be computed only for patients with osimertinib discontinuation (ie. those with calculated stop date of second-line therapy).

Other patients will be considered as censored observations. The following situations might be observed:

- alive patients at end of observation, ie. those with [PI. PI_pt_class] = “Living patient”. For these patients, the time to censoring will be computed as the difference between the end of observation date (as defined later) and the start date of afatinib / stop date of osimertinib therapy (depending on the type of OS evaluated) + 1 day;
- untraceable patients at end of observation, ie. those with [PI. PI_pt_class] = “Untraceable patient”. For these patients, the time to censoring will be computed as the difference between the latest date when the patient was known to be alive (ie. [PI. PI_date_alive]) and the start date of afatinib / stop date of osimertinib therapy (depending on the type of OS evaluated) + 1 day.

End of observation date

- For alive patients (ie. those with [PI. PI_pt_class] = “Living patient”), it will correspond to the “Date of data collection (dd/mmm/yyyy)” [PI. PI_date_coll]
- For deceased patients (ie. those with [PI. PI_pt_class] = “Deceased patient”) it will correspond to the “Date of death (dd/mmm/yyyy)” [PI. PI_date_death]
- For untraceable patients (ie. those with [PI. PI_pt_class] = “Untraceable patient”) it will correspond to the “Date patient last known to be alive (dd/mmm/yyyy)” [PI. PI_date_alive]

Duration of observation window (in months) starting from the first-line treatment start

- For alive patients (ie. those with [PI. PI_pt_class] = “Living patient”), it will be calculated as the difference between the end of observation date (as defined before) and Start date of first-line therapy (as defined before) + 1 day
- For deceased patients (ie. those with [PI. PI_pt_class] = “Deceased patient”) it will be calculated as the difference between the end of observation date (as defined before) and Start date of first-line therapy (as defined before) + 1 day

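### Patients recorded as still on treatment are censored at the end of observation, not at the date last verified on treatment as the protocol requires, so time on treatment can include unobserved event-free time

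*SAP*

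**What the plan says.** Protocol 9.7 sets one censoring rule for time on treatment: "Patients who were not known to have discontinued treatment will be censored on the date they were last verified to have been on treatment".

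SAP chapter 3 uses a different date for the group it describes as "non-deceased patients with evidence of ongoing treatment at end of observation". Operationally these are living or untraceable patients whose latest dose record has *Treatment discontinued?* set to No. For them, "the time to censoring will be computed as the difference between the end of observation date (as defined later) and the start date"; that start belongs to the index therapy (uncommon cohort) or to first-line therapy (sequencing cohort). Time to second-line treatment failure follows the same pattern, triggered by *Ongoing at end of observation?* set to Yes.

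The end of observation date is defined later in the same chapter:

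- Living patients: "For alive patients (ie. those with [PI. PI_pt_class] = “Living patient”), it will correspond to the “Date of data collection (dd/mmm/yyyy)”".
- Untraceable patients: "For untraceable patients (ie. those with [PI. PI_pt_class] = “Untraceable patient”) it will correspond to the “Date patient last known to be alive (dd/mmm/yyyy)”".

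A separate group, "non-deceased patients with unknown information on treatment interruption at end of observation", is censored earlier, at the latest start date among its dose records (or line start, for second-line failure).

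For overall survival the SAP censors living patients at end of observation and untraceable patients at "the latest date when the patient was known to be alive (ie. [PI. PI_date_alive)". The protocol gives no censoring date specific to survival.

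**The concern.** The study reads existing records, and Protocol 9.2 adds that "Data extraction from local data bases might be used when possible". A chart or database shows treatment up to its last visit or prescription, which may precede the day of abstraction. The variables listed in Protocol 9.3 include start and end dates of each line and date of death, but no last-visit, last-prescription or last-on-drug date. A No in the discontinuation field is therefore an undated status as far as the documents show.

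If a patient stopped after the last record entry and the stop was not captured, the SAP rule keeps that patient at risk and event-free until abstraction. For an untraceable patient marked No, being alive on a date does not show that the drug was still being taken then.

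At stake are the Kaplan-Meier quartiles of the primary endpoint in both cohorts and of second-line failure in the uncommon cohort.

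**Working it through.** **1. The plan's own figure.** Protocol Table 9.5:1 gives an expected 95% CI width of 13.7 months (80th percentile 16.2) for 200 patients, median 30 months and 10% censoring. Without censoring, with hazard ln 2 / 30 = 0.0231 per month, the width is about 2 × 1.96 × √(0.25/200) / (0.0231/2) = 12.0 months. Simulating with a random 10% of event times relabelled as censored gives 13.5 and 16.0, so the table is reproduced within about 2%. It does not depend on the disputed date and serves here only as a yardstick.

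**2. Direction.** The Kaplan-Meier estimate is S(t) = Π(1 − d_j/n_j). For the same recorded events, both rules share every d_j. Later censoring makes each n_j equal or larger, so the SAP curve is never below the protocol curve. Whether the excess is bias depends on whether stops in the gap were recorded:

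- none recorded: last-verified censoring is the sound choice and the SAP rule is too high;
- all recorded: the SAP rule is sound;
- status confirmed at end of observation: the dates coincide and the difference is zero.

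**3. How many stops a gap can hide.** With exponential times and a 30-month median, the chance of stopping within g months of the last record is 1 − 2^(−g/30): 6.7% for 3 months and 12.9% for 6.

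**4. Size, varying gap.** Assumptions: afatinib Weibull (shape 1.3, median 13 months) plus osimertinib exponential (median 12 or 16); collection uniform 9.5 to 45 months after osimertinib start; last on-drug date uniform 0–3 or 0–6 months before collection; no stop in the gap recorded; 400,000 patients per scenario. SAP rule minus protocol rule, sequencing cohort:

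| Gap | Median | Upper quartile |
|---|---|---|
| 0–3 months | +0.2 to +0.4 | +0.8 to +1.4 |
| 0–6 months | +0.6 to +0.9 | +1.9 to +3.4 |

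The ends of the median range are 29.65 − 29.42 = 0.23 and 35.19 − 34.26 = 0.93. In the uncommon cohort (assumed median 12, follow-up uniform 11.5 to 60 months) the median moves +0.04 or +0.2 and the upper quartile +0.5 or +1.3.

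**5. Size, fixed gap.** Assumptions: exponential times, starts uniform 12–60 or 24–72 months before collection, and 25% or 100% of event-free patients unverified at collection.

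| Gap | Sequencing median (true 30) |
|---|---|
| 0 | 0.0 |
| 1 month | 0.0 to +0.5 |
| 3 months | +0.1 to +1.7 |
| 6 months | +0.3 to +4.4 |

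The +4.4 needs every event-free patient to be unverified for a full 6 months. The uncommon-cohort median (assumed 12) moves 0.0 to +0.5 throughout.

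**6. Survival, for contrast.** Assume exponential survival with median 30 months, follow-up uniform 11.5 to 60 months, and all deaths up to collection recorded. Data-collection censoring gives 30.1. Censoring survivors at last contact gives 29.4 (gap 0–3) or 28.6 (gap 0–6). With half of the gap deaths recorded and a 0–6 gap, the results are 30.9 and 29.3, errors of similar size on opposite sides.

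**The case against.** The SAP does separate patients by what is known. No applies to patients described as having evidence of ongoing treatment at end of observation, and those with unknown status are cut back to their latest dose-record start. For second-line failure the field itself asks about status at end of observation. The eCRF and its completion rules are not among the documents, so an undocumented check cannot be ruled out. If No was confirmed on the collection date, the SAP and the protocol agree. This stands: it makes the bias conditional. It does not remove the mismatch, because neither the SAP algorithm nor the protocol's variable list ties the status to a date, and the date last known alive is not an on-drug date.

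It also stands that the shift is small beside sampling error in the ordinary scenarios (0.9 against a width of 13.7 months is 0.9/13.7 = 7%), and that the study is descriptive with no comparisons.

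A reader might infer that survival has the same defect, and more severely because more patients are censored. The documents do not support that. The protocol's sentence concerns treatment and sets no survival censoring date; untraceable patients are already censored at the date last known alive; and nothing says that living status was assigned without a check. Deceased patients enter by date of death, without needing a visit, so late deaths can be captured. Step 6 shows that last-contact censoring then biases survival downward. The same asymmetry can affect time on treatment where gap stops or deaths are captured, which is why both rules should be reported.

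**Conclusion.** The SAP departs from Protocol 9.7 on the censoring date for time on treatment in both cohorts, and uses the same date for second-line failure, without giving a reason. The bias is zero if treatment is confirmed at end of observation and generally upward if it is not. On assumed gaps of up to 3 or 6 months it is roughly 0.2 to 0.9 months on a sequencing median near 30, and about 4 months only in the extreme case. The uncommon-cohort median is little affected; upper quartiles shift more. Every size rests on an assumed gap, an assumed share of unverified patients and unrecorded stops in the gap, none of which the documents give. A reader who concludes that the results are certainly inflated, or that survival is the main casualty, goes further than the documents allow.

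**What to change.** In SAP chapter 3, under both time-on-treatment definitions and time to second-line failure, censor ongoing patients at the last documented date on drug on or before data collection. Apply this also to untraceable patients marked No. Where treatment was confirmed on the collection date, that is the date to use. Report the current end-of-observation rule as a sensitivity analysis: with otherwise independent censoring, the two results bracket the answer under partial capture of stops.

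For overall survival, keep data-collection censoring for living patients whose vital status is confirmed at that date, and state that this is what living means. Use the date last known alive only where it is not confirmed. Do not move all living patients to last contact.

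The cost is revised SAP wording, one extra date per ongoing patient from a record already being abstracted (assuming the eCRF does not already hold it), and slightly shorter recorded follow-up.
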